## **5. Materials and method:**

**5.1. Type of study:** Randomized controlled trial

**5.2 Place of Study:** Department of Nephrology, Chittagong Medical College Hospital, Chattogram, Bangladesh.

**5.3 Study period:** One and half year from acceptance of protocol.

**5.4 Study population:** The study population will include adult hemodialysis patients with secondary hyperparathyroidism attending in the Nephrology department, CMCH will be the study population during the study period.

**5.5 Sampling technique:** Consecutive sampling. From the Selected participants, the intervention and control will be randomly assigned in a 1:1 ratio (block size of four) through computer- generated randomization.

**5.6 Inclusion criteria:**

1. Adult patients aged 18 years or older.
2. Diagnosed with secondary hyperparathyroidism (SHPT) with elevated serum PTH levels ( $>300$  pg/mL).
3. Undergoing maintenance hemodialysis for at least 3 months.
4. Patients on calcitriol therapy after washout period of 40 hrs.

**5.7 Exclusion criteria:**

1. Patients with known case of primary hyperparathyroidism or parathyroidectomy.
2. Serum calcium  $>10$  mg/dL or phosphate  $>5.5$  mg/dL at baseline.
3. Active liver disease or significant hepatic dysfunction, Alcoholism.
4. History of hypersensitivity to vitamin D analogs.
5. Pregnant or breastfeeding women.
6. Concurrent use of medications (e.g. bisphosphonates).
7. Patients with active malignancy (e.g. multiple myeloma, bronchogenic carcinoma).

### 5.8. Sample size:

To calculate sample size for case control, study the comparison between two means, the following formula was followed (Hoque, 2014)

$$n = \frac{(Z_a + Z_b)^2 \cdot (s_1^2 + s_2^2)}{(m_1 - m_2)^2}$$

Here,

$m_1$  = 342.0 (mean of iPTH in oral cholicalciferol group)

$m_2$  = 279.0 (mean of iPTH in intravenous doxercalciferol group)

$s_1$  = 42.0 (Standard deviation of oral cholicalciferol group)

$s_2$  = 90.0 (Standard deviation of intravenous doxercalciferol group)

$Z_a$  = Z value (two tail) of standard normal distribution at 95% confidence level or 5% level of significance = 1.96 (when  $\alpha = 0.05$  at 5% level of significance)

$Z_b$  = Z value at 90% power = 1.28 (when  $\beta = 0.1$  and Power =  $1 - \beta$ )

Therefore,

$$\begin{aligned} n &= \frac{(1.96 + 0.85)^2 \cdot \{(42.0)^2 + (90.0)^2\}}{(342.0 - 279.0)^2} \\ &= 42.8 \end{aligned}$$

This study is a follow-up study, necessitating a 15% increase in the sample size to compensate for dropout cases during the follow-up period. Consequently, the total sample size amounted to 49 cases, comprising 43 estimated sample size plus an additional 6.

Therefore, total sample size was 98 ( $49 \times 2$ ).

All values were taken from Aggarwal et al. (2011).

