disorder (CKD-MBD), which includes pain, fractures, soft tissue calcifications, and increased mortality due to cardiovascular events(Shah et al. 2024; Salera et al. 2025). Additionally, higher iPTH levels correlate with increased uric acid and systemic inflammation in patients with cardiovascular disease (CVD), reinforcing the systemic impact of PTH dysregulation (Checa-Roset al. 2025).

Intravenous doxercalciferol and oral calcitriol are both active vitamin D analogs used to manage secondary hyperparathyroidism (SHPT) in hemodialysis patients, but they differ in pharmacologic properties and clinical application. Oral calcitriol, the active form of vitamin D, binds directly to vitamin D receptors, effectively lowering parathyroid hormone (PTH) levels but often at the cost of increased serum calcium and phosphate levels, leading to higher vascular calcification risk (Thadhani et al., 2020). In contrast, doxercalciferol, a synthetic vitamin D analog, is a prodrug requiring hepatic activation. When administered intravenously, it produces a more stable PTH suppression with fewer calcemic side effects (Yang et al., 2025). A recent randomized trial found that doxercalciferol suppressed PTH by over 40% in 72.5% of patients compared to 58% in the calcitriol group (Yang et al., 2025), with SHPT prevalence reaching 86% in dialysis cohorts (Thadhani et al., 2020). Clinical preference now favors intravenous doxercalciferol in dialysis due to its dosing control and reduced hypercalcemia risk.

Recent clinical trials and meta-analyses have provided comparative insights into the effectiveness of calcitriol and doxercalciferol in managing secondary hyperparathyroidism in hemodialysis patients. A multicenter phase II trial revealed that intravenous doxercalciferol suppressed parathyroid hormone (PTH) levels by over 40% in 72.5% of patients, compared to 58% for oral calcitriol (Yang et al., 2025). Moreover, a recent meta-analysis indicated that doxercalciferol was associated with a significantly lower risk of hypercalcemia compared to calcitriol (Abreu et al., 2021). In practical terms, the prevalence of secondary hyperparathyroidism in hemodialysis patients is approximately 86% (Thadhani et al., 2020). Additionally, evidence suggests that calcitriol effectively reduces PTH but leads to higher serum calcium and phosphate levels, increasing vascular calcification risks, while

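### Section 5.8 does not reproduce: it declares 90% power, substitutes an 80% Z value, and prints 42.8 per arm where its own line gives 19.6

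*Protocol*

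**What the plan says.** Protocol section 5.8 uses the two-means formula n = (Za + Zb)² (s1² + s2²) / (m1 − m2)². It lists these inputs:

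- Significance: "Z value (two tail) of standard normal distribution at 95% confidence level or 5% level of significance = 1.96".
- Power: "Z value at 90% power = 1.28".
- Comparator mean and SD: "342.0 (mean of iPTH in oral cholicalciferol group") and "42.0 (Standard deviation of oral cholicalciferol group").
- Experimental mean: "279.0 (mean of iPTH in intravenous doxercalciferol group"), with an SD of 90.0.

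The worked line then puts 1.96 + 0.85 in the bracket, keeps SDs of 42.0 and 90.0 and the difference 342.0 − 279.0, and prints 42.8. The dropout step reads: "Consequently, the total sample size amounted to 49 cases, comprising 43 estimated sample size plus an additional 6". Doubling gives 98. All values are attributed to one 2011 study, which is not in the reference list (section 5.16).

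The control treatment elsewhere is oral calcitriol: see the research question (3.1), the randomisation paragraph in 5.11, and the treatment paragraph that follows it.

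**The concern.** This is the protocol's only justification for its size, and three of its elements disagree: the declared power, the Z value substituted, and the printed result. A reader who repeats the calculation gets neither 42.8 nor 90% power. Separately, the label on the comparator inputs names a drug that neither arm is assigned. If the label is accurate, the 63 pg/mL difference and the SD of 42 describe another contrast and need justification before they are used for doxercalciferol against calcitriol. At stake is whether an ethics committee or a later reader can rely on the 90% figure.

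**Working it through.** **Inputs, all from section 5.8.** m1 = 342.0, m2 = 279.0, difference 63.0, 63² = 3969. s1 = 42.0, s2 = 90.0, s1² + s2² = 1764 + 8100 = 9864. Za = 1.96. Zb = 1.28 as declared (Φ(1.28) = 0.900), 0.85 as substituted (Φ(0.85) = 0.802).

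**Step 1: the plan's own figure.**

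| Zb | SDs | Calculation | n per arm |
|---|---|---|---|
| 0.85 (worked line) | 42, 90 | 2.81² × 9864 / 3969 | 19.62 |
| 1.28 (declared) | 42, 90 | 3.24² × 9864 / 3969 | 26.09 |
| Printed result | | | 42.8 |

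Neither reproduces. Nor do other readings of the same inputs: one-sided alpha gives 15.5 (Zb 0.85) or 21.3 (Zb 1.28), and doubling to a total gives 39.2 or 52.2.

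**Step 2: where 42.8 might come from.** With Zb = 1.28 and SD 90 in both arms, 3.24² × (8100 + 8100) / 3969 = 42.85. This uses only numbers that appear in the section, so it is a plausible source. It is not the only one. Zb = 1.28 with the printed SDs and a difference of 49.2 gives 42.78. Zb = 0.85 with s1 = 115.8 gives 42.79, and Zb = 0.85 with s2 = 140.5 gives 42.78. The protocol states none of these.

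**Step 3: power of the planned size for 63 pg/mL, two-sided 5%.** In the normal approximation, power = Φ(63 / √((s1² + s2²)/n) − 1.96). The t-based value uses the noncentral t with Welch degrees of freedom.

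| Evaluable per arm | SDs 42, 90: normal / t | SDs 90, 90: normal / t |
|---|---|---|
| 43 | 98.6% / 98.3% | 90.1% / 89.4% |
| 42 | 98.4% / 98.1% | 89.4% / 88.7% |
| 41 | 98.2% / 97.9% | 88.7% / 87.9% |

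For example, with SDs 42 and 90 and n = 43: 63 / √(9864/43) = 4.16, and Φ(4.16 − 1.96) = 0.986.

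**Step 4: dropout.** 43 × 0.15 = 6.45, entered as 6, so 49. Loss that still leaves 43: 6/49 = 12.2%. At 15% loss, 49 × 0.85 = 41.65, so 41-42 remain. Keeping 43 after 15% loss needs 43/0.85 = 50.6, or 51 per arm.

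**Step 5: sensitivity at 43 per arm (assumed values, normal approximation).**

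- Printed SDs, difference 50, 45, 40 or 30 pg/mL: power 91%, 84%, 75% or 51%.
- Difference 63 pg/mL, common SD 100, 120 or 150: power 83%, 68% or 50%.

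These show how far power depends on the inputs. They do not predict what the trial will see.

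**The case against.** The strongest reply is that the error does no harm. The printed n exceeds what the formula requires at either Z value, so on the printed inputs the trial has more power than it claims. If the SD was meant to be 90 in both arms, 43 per arm gives almost exactly 90%, and 0.85 and 42.0 are then transcription slips. That stands as an argument against any claim that the arithmetic leaves the trial short. It does not make the section consistent, because the line as printed still gives 19.6.

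The dropout step can also be defended. The plan says it raises the number by 15%, and it does so, apart from rounding 49.45 down to 49. It does not claim that 43 will remain after 15% loss. This part is minor.

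Some stronger readings are tempting and are not supported:

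- **That s1 = 42 was certainly not used.** Step 2 shows other input changes that also reach 42.8.
- **That the effect certainly comes from another comparator.** The protocol shows a label, "mean of iPTH in oral cholicalciferol group". It may be a naming slip, and the 2011 source is not at hand.
- **That real power is near 44%.** Section 1 reports that "doxercalciferol suppressed PTH by over 40% in 72.5% of patients compared to 58% in the calcitriol group". Turning those rates into a standardised difference of about 0.40 assumes normally distributed percent change with equal SDs, and it concerns a different endpoint from mean iPTH.
- **That power is 16-49% because the SD will be 150-300.** Those SDs appear nowhere in the protocol. Entry above 300 pg/mL with no upper limit is a reason to justify the SDs, but it does not establish those values.
- **That a null result could not be interpreted.** It would be read from the estimate and its confidence interval.

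**Conclusion.** The point holds as a failure of the calculation to reproduce, together with an unresolved comparator label. The declared 90%, the substituted 0.85 and the printed 42.8 cannot all be right with the printed means and SDs: the line gives 19.6 per arm, or 26.1 at the declared power.

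A reader might infer that the trial is underpowered. The arithmetic does not show that. If the true difference is 63 pg/mL and 43 per arm are evaluable, power is about 98% with SDs 42 and 90 and about 89-90% with SD 90 in both arms. At 15% loss the second figure is about 88-89%. All of this rests on the 63 pg/mL difference and on SDs that the protocol does not justify for doxercalciferol against calcitriol.

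Severity: should be fixed. The stated power needs a derivation that works, but nothing here shows that the sample size must change.

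**What to change.** Keep 98 patients and rewrite section 5.8:

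1. Use one Zb throughout; 1.28 if 90% power is meant.
2. Reconcile s1, s2 and the printed n. If an SD of 90 was intended in both arms, say so and why. If 42 and 90 are right, print 26.1 and explain why more patients are randomised.
3. Correct the comparator label if it is a slip. Otherwise justify the inputs for calcitriol against doxercalciferol, or say that a surrogate comparator was used. Add the 2011 source to the references.
4. Restate the power that 49 randomised per arm gives under the corrected inputs, with a short range over the SD and the difference, marked as assumptions.
5. State that 49 per arm leaves 43 evaluable up to about 12% loss, and 41-42 at 15%.

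The cost is protocol wording only, with no added patients, visits or tests. Depending on the SDs adopted, the stated power may move up or down from 90%.

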### 5.9 List of Variables

Variables	Type	Value	Expression
Sociodemographic Variables			
Age	Discrete	In completed years	Mean $\pm$ SD
Sex	Categorical	Male / Female	Frequency (%)
Monthly income	Continuous	In local currency (BDT/USD)	Mean $\pm$ SD / Median (IQR)
Height	Continuous	In centimeters (cm)	Mean $\pm$ SD
Weight	Continuous	In kilograms (kg)	Mean $\pm$ SD
BMI	Continuous	In kg/m 	Mean $\pm$ SD
Clinical Variables			
Diabetes Mellitus (DM)	Categorical	Present / Absent	Frequency (%)
Hypertension (HTN)	Categorical	Present / Absent	Frequency (%)
Blood pressure	Continuous	In mmHg	Mean $\pm$ SD
Duration of Hemodialysis	Continuous	In months or years	Mean $\pm$ SD
Biochemical Variables			
Serum Calcium (S. Ca)	Continuous	In mg/dL	Mean $\pm$ SD
Serum Phosphate (Po4)	Continuous	In mg/dL	Mean $\pm$ SD
Parathyroid Hormone (PTH)	Continuous	In pg/mL	Mean $\pm$ SD

**Operational definitions:**

**Parathyroid Hormone (PTH):** Parathyroid Hormone (PTH) will be measured as intact PTH (iPTH) in picograms per milliliter (pg/mL) using a second-generation immunoassay. In accordance with KDIGO recommendations, for patients receiving maintenance hemodialysis, iPTH levels sustained above 300 pg/mL are considered indicative of secondary hyperparathyroidism (SHPT).

**Doxercalciferol:** Doxercalciferol will be administered intravenously post-hemodialysis in doses ranging from 1–4 micrograms per session. Its use will follow KDIGO recommendations for selective vitamin D receptor activator (VDRA) therapy to suppress iPTH levels while minimizing the risk of hypercalcemia and hyperphosphatemia in dialysis patients.

**Calcitriol:** Calcitriol will be administered orally on a daily or alternate-day schedule, titrated based on iPTH, calcium, and phosphate levels.

**Maintenance Hemodialysis:** Maintenance hemodialysis is defined as a twice-weekly dialysis regimen maintained for a minimum duration of three months in patients with end-stage kidney disease, consistent with KDIGO standards for long-term renal replacement therapy.

**Secondary Hyperparathyroidism (SHPT):** Secondary hyperparathyroidism (SHPT) is defined as a chronic elevation of iPTH above 300 pg/mL in patients undergoing maintenance hemodialysis, with supporting evidence of disrupted calcium, phosphate, and vitamin D metabolism as outlined in KDIGO guidelines for CKD-MBD.

**Adverse Events:** An AE is defined as any untoward medical occurrence in a clinical trial patient during the study, the event does not necessarily have a causal relationship with that treatment. Therefore, an AE can be any unfavorable and unintended sign (including any clinically significant abnormal laboratory finding), symptoms, or disease, temporally associated with using a medicinal product.

**Major adverse events:** Will defined as any event leading to admission or prolonged admission, anaphylactic reactions, withdrawal, or death.

**Minor adverse events:** Will defined as minor if it does not require admission to the hospital or withdrawal of the drug. Such as nausea, vomiting, edema, headache, fatigue, metallic test, loss of appetite, constipation.

**Withdrawal criteria:**

- Drug intolerance or patient refusal to continue medication due to adverse effects like nausea, anorexia, vomiting, etc.
- The patient wanted to withdraw himself from the study.
- If any participant became pregnant during the study period.

**5.10 Data collection instrument:** A structured pretested case record form.

**5.11 Data collection procedure:**

All ESRD patients on hemodialysis will be consecutively and prospectively screened according to the above inclusion and exclusion criteria to identify eligible participants for randomization. Eligible patients and their legal relatives will then fully explain the study protocol, their role in the study, and the risks of the study. They will be informed of their right to withdraw from the study at any stage. After getting written informed consent, they will be finally enrolled in the study.

- **Baseline evaluation:** Baseline data will be collected at enrollment, including demographic and anthropometric variables such as age, sex, monthly income, height, weight, and body mass index (BMI). These variables will be recorded systematically for both groups to ensure proper group characterization and comparability. In addition, clinical information will be documented, focusing on the presence of comorbidities such as diabetes mellitus (DM) and hypertension (HTN). Baseline serum calcium, serum phosphate, iPTH will be recorded in the case record form. washout period of calcitriol will be conducted prior to randomization.
- **Randomization:** After consenting, eligible individuals will be recruited consecutively and randomly assigned in 1:1 ratio (block size of four), with a computer-generated randomization list, to one of the two treatment arms (Experimental group and Control group). Group 1 (Control Group) Will received oral calcitriol alone with standard treatment of CKD. Group 2 (Experimental Group) will received post-hemodialysis intravenous (IV) doxercalciferol alone with standard treatment of CKD. All participants, regardless of group allocation, who are on calcium acetate or sevelamer will continue these medications at their existing doses throughout the study period.
- **Blinding:** Blinding of the study medication is not possible because of resource limitations. It is an open-label study and both the researcher and the subject know about the drugs they are receiving.

**Sample Collection procedure:** Blood samples will be collected pre-dialysis after an overnight fasting period, with all aseptic precaution 5 mL of venous blood drawn into appropriate vacutainers.

- iPTH will be measured using a chemiluminescence immunoassay (CLIA).
- Serum calcium and phosphate will be analyzed using colorimetric methods on a Beckman Coulter AU480 or equivalent validated clinical chemistry analyzer.

All laboratory analyses will be conducted in an ISO-certified laboratory, ensuring accuracy and standardization of results.

**Treatment:** The treatment phase will last for twelve weeks. Experimental subjects will receive an intravenous loading dose of doxercalciferol 4 micrograms after dialysis, in addition to their standard routine medications. Each Dose of doxercalciferol will be given after skin sensitivity test. Skin sensitivity test will be performed by a small amount of doxercalciferol inject intradermally → wait 10-15 minutes → see for localized swelling and redness. Though skin sensitivity test negative despite patients may developed anaphylactic reaction, Then following measure will be taken. Prevent further contact with allergen, ensure airway patency, anti histamine, hydrocortisone, nebulize with sulbutamol, adreline, i/v fluids. Patients in the control group will receive oral calcitriol 0.25 micrograms once daily, along with their standard routine medications.

**Evaluation of the patient at 6 Weeks:** The patients will be followed up at 6 weeks ( $\pm 2$  days) and will instructed to report immediately in case of any advance events following consumption of the drug. Tolerability will be assessed using an adverse event profile (adverse events, serious adverse events). Safety population consist of subjects who receive at least one dose of study medication. Body weight and sitting blood pressure will be evaluated. patients will be removed if any of the withdrawals mentioned above are observed, and appropriate management will be initiated in the nephrology department of CMCH.

**Follow –up and outcome assessment:** All the patients will be examined again after 12 weeks ( $\pm 2$  days) The same biochemical parameters—serum calcium, serum phosphate, iPTH,—will be reassessed under the same collection and analysis protocols. These follow-up results will be compared with baseline values to evaluate the relative efficacy of IV doxercalciferol versus oral calcitriol in controlling SHPT and maintaining mineral balance. All data, including demographic, clinical, and laboratory results, will be systematically documented in a Case Record Form (CRF) to ensure completeness and integrity of the dataset.

- If a patient does not return for a scheduled visit, every effort will be made to contact the patient. If possible, every effort will be made to document patient outcomes in any circumstance. The Investigator will enquire about the reason for withdrawal, request that the patient return all unused study medication, ask that the patient return for a final visit, if applicable, and follow up with the patient regarding any unresolved adverse events.

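### The protocol fixes and prints a block size of four in a single-centre open-label trial, so about a third of allocations can be deduced by anyone who recruits and tracks past ones

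*Protocol*

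**What the plan says.** Section 5.5 (Sampling technique) says that participants will be "randomly assigned in a 1:1 ratio (block size of four) through computer- generated randomization". Section 5.11 (Randomization) repeats it: "randomly assigned in 1:1 ratio (block size of four), with a computer-generated randomization list". Both places give one block size. Neither mentions strata, varying sizes or keeping the size from recruiters.

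The Blinding paragraph of 5.11 says: "It is an open-label study and both the researcher and the subject know about the drugs they are receiving". Section 5.2 names one site, "Department of Nephrology, Chittagong Medical College Hospital, Chattogram, Bangladesh", so there is a single sequence to follow. Section 5.8 sets the total: "Therefore, total sample size was 98".

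Three stated steps bear on selective entry:
- Recruitment is consecutive and follows consent: "After consenting, eligible individuals will be recruited consecutively".
- The calcitriol washout is placed before randomisation (5.11, Baseline evaluation).
- The Data and Safety Monitoring Plan contains a monthly table of patients approached, eligible and randomised.

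The text available names no holder of the list and no concealment method. The flow chart (5.15) is not shown, so its content is unknown.

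**The concern.** In a permuted block of known size, the remaining allocations are fixed once one arm is used up. With blocks of four, the fourth place is always determined, and the third is determined too when the first two match. Masking would hide past allocations and so protect the sequence, but this trial has none. A single unstratified list at one site is also easy to follow.

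At stake is selection at entry. Someone who can work out the next arm can bring a patient forward or hold one back, deliberately or not, through the timing of the consent discussion or of the washout. The expected direction is declared: 3.2 hypothesises that doxercalciferol is the more effective drug, and 5.13 foresees results that may favour it. An objective laboratory endpoint such as iPTH limits bias in assessment but does nothing about who enters which arm. Selection on traits that are not recorded, such as expected adherence, could not be adjusted away afterwards.

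**Working it through.** The protocol gives no predictability figure, so there is none to reproduce.

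**Inputs.** 1:1 ratio and block size 4 (5.5, 5.11); one site (5.2); open label (5.11); total 98 (5.8). Assumption: the recruiter knows the block size and the order of past allocations.

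**Step 1, certain allocations per block.** The six equally likely sequences are AABB, BBAA, ABAB, BABA, ABBA and BAAB. An allocation is deducible when the earlier ones in its block have used up one arm.
- AABB and BBAA: places 3 and 4, so 2 each.
- The other four: place 4 only, so 1 each.
- Expected number = (2 × 2 + 4 × 1)/6 = 8/6 = 4/3 per block, or 33.3%.

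The general formula for m patients per arm in a block, 2m/(m + 1), agrees: m = 2 gives 4/3.

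**Step 2, over the trial.** 98 = 24 × 4 + 2. The 24 full blocks give 24 × 4/3 = 32. The last two patients occupy places 1 and 2 of an incomplete block and add none. So 32 of 98 = 32.7%.

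**Step 3, best guess.** The recruiter always guesses the arm that is behind in the block. The chance of being right, by place:
- Place 1: 1/2.
- Place 2: 2/3.
- Place 3: (1/3) × 1 + (2/3) × (1/2) = 2/3.
- Place 4: 1.

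The sum is 2.833 of 4, or 70.8%. Over 98 patients: 24 × 2.833 + 1/2 + 2/3 = 69.2, or 70.6%.

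**Step 4, alternatives.** Fixed sizes were enumerated over full blocks. Mixed sizes were simulated (2,000 runs, 98 patients) with an observer who knows which sizes are in use but not their order.

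| Block scheme | Deducible with certainty | Best guess correct |
|---|---|---|
| Fixed 4 | 33.3% | 70.8% |
| Fixed 6 | 25.0% | 68.3% |
| Fixed 8 | 20.0% | 66.6% |
| Mixed 4 and 6 | 5.5% | 69.2% |
| Mixed 4, 6 and 8 | 2.2% | 67.9% |

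On 98 patients, the mix of 4, 6 and 8 lowers certain allocations from 32 to about 2 (0.022 × 98 = 2.2). Correct guesses fall only from 69.2 to about 66.5 (0.679 × 98).

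**The case against.** **Who knows what.** The protocol does not say who screens, who enrols or who holds the list. It says that the researcher knows the drugs given. A reader might infer that the recruiter actually knows a third of the allocations in advance; the documents do not support that. The allocations are deducible, by someone who recruits and keeps count in order. This objection stands and sets the wording of the point.

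**Existing safeguards.** Consecutive screening of all haemodialysis patients, consent and washout before randomisation, and the monthly log all reduce the leeway, and the log could reveal eligible patients who were not randomised. This stands in part. The timing of consent and washout remains with trial staff, who in an open-label trial can know past allocations. The log holds monthly counts with no column for why an eligible patient was not randomised.

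**Repair in the analysis.** A reader might infer that no analysis could correct the harm. That is too broad. Baseline iPTH is recorded, so selection on it would be visible and could be adjusted for. The limit applies to unmeasured traits.

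**Concealment.** A reader might infer that the list is open to the recruiter. The text is only silent on this, and the flow chart is not shown. What the protocol positively fixes is the single disclosed block size, and the point rests on that.

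**Remedy.** Varying the blocks barely lowers best-guess success, and envelopes cannot stop inference from past open allocations. This is correct, and the benefit has to be stated accordingly.

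**Final balance.** A reader might add that 98 is not a multiple of four. With blocks of four the worst split is 50:48, which is trivial and not a defect.

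**Conclusion.** The concern holds as a weakness of the stated design. A single block size of four, printed in 5.5 and 5.11 of a single-centre, unstratified, open-label trial, leaves an expected 4/3 of every 4 allocations deducible (about 32 of 98), and about 71% can be guessed correctly.

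The figures assume a recruiter who knows the block size and tracks allocations in order. One third is an average: each full block has either one or two deducible places. For full blocks the share does not depend on the total sample size.

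The arithmetic is certain; the practical impact is less so, because the stated safeguards narrow the opportunity by an unknown amount. A reader might infer that selection bias is present. Nothing in the protocol shows that, and the point claims only an avoidable opportunity. The change is worth making because it is cheap and because selection on unmeasured traits cannot be undone later.

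**What to change.** 1. Delete the block size from 5.5 and 5.11. State only that block sizes vary at random and are known solely to the person who generates the list.
2. Generate the list with randomly varying blocks, for example of 4, 6 and 8.
3. Have a colleague who does not recruit hold the allocations, for example in sequentially numbered opaque sealed envelopes. Release each one only after consent, eligibility and baseline sampling are recorded.

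Steps 1 and 2 limit deduction from past allocations. Step 3 keeps the list itself out of view and fixes the patient's entry before the arm is revealed. All three are needed, and together they still leave best-guess success near 68%.

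The cost is a short protocol change, a new list and about 98 envelopes. It assumes that a suitable colleague is available, which the documents do not state. The final split may move slightly further from 49:49: an incomplete last block of eight could give 51:47 at worst. If recruitment has begun, which the documents do not show, the change can apply only to the remaining allocations.

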### **Specific objectives:**

1. To detect and compare the reduction of serum parathyroid hormone (PTH) levels following treatment with intravenous doxercalciferol and oral calcitriol in hemodialysis patients.
2. To assess the changes in serum calcium and phosphate levels associated with each treatment modality.
3. To evaluate the incidence of treatment-related hypercalcemia and hyperphosphatemia in both treatment groups.
4. To compare the adverse events and efficacy profiles of intravenous doxercalciferol and oral calcitriol in the management of secondary hyperparathyroidism in hemodialysis patients.

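### Calcium acetate and sevelamer doses are frozen for the full 12 weeks with no safety exception, although both arms take active vitamin D and calcium and phosphate are scheduled only at baseline and week 12

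*Protocol*

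**What the plan says.** The binder rule stands in section 5.11, under Randomization: "All participants, regardless of group allocation, who are on calcium acetate or sevelamer will continue these medications at their existing doses throughout the study period". It covers both arms and the whole of each patient's participation, and it states no condition.

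The study drugs have some flexibility. Under Operational definitions, calcitriol is "titrated based on iPTH, calcium, and phosphate levels", and "Doxercalciferol will be administered intravenously post-hemodialysis in doses ranging from 1–4 micrograms per session". Section 5.7 excludes patients with baseline calcium above 10 mg/dL or phosphate above 5.5 mg/dL.

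The laboratory schedule has two points. Calcium, phosphate and iPTH are measured at baseline and again at week 12. The week-6 visit covers adverse events and adds: "Body weight and sitting blood pressure will be evaluated". It lists no blood test.

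Calcium and phosphate are also outcomes. The second specific objective concerns their changes, and the third reads: "To evaluate the incidence of treatment-related hypercalcemia and hyperphosphatemia in both treatment groups".

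**The concern.** Both arms take active vitamin D, and the protocol's own Introduction says that calcitriol tends to raise calcium and phosphate. Calcium acetate is a further source of calcium. If a patient's calcium rises, reducing or switching that binder is an obvious response; if phosphate rises, raising sevelamer is. The rule as written permits neither.

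What is at stake is mainly safety. An investigator who follows the text must leave the binder unchanged or remove the patient from the trial. Removal also puts the week-12 result at risk. A second, smaller matter is interpretation. Calcium and phosphate are study outcomes that binders affect, and nothing in the protocol records whether the freeze was kept.

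**Working it through.** The protocol gives no figure to reproduce on this point. The check sets the relevant sections side by side.

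**1. Is there an exception anywhere?**
- Section 5.11, Randomization: the binder sentence contains none.
- Operational definitions: the titration wording concerns calcitriol, and the dose range and the aim of limiting hypercalcaemia concern doxercalciferol. Neither mentions binders.
- Withdrawal criteria: intolerance or refusal because of adverse effects, the patient's own wish, and pregnancy. None is a calcium or phosphate criterion.
- Section 5.11, 6-week evaluation: the provision for management applies to patients removed under those criteria.
- Section 5.11, missed visits, and the Data and Safety Monitoring Plan with its tables: no binder provision.

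**2. What would trigger an exception?** Scheduled calcium and phosphate results per patient: baseline + week 12 = 2. The first falls before treatment and the second at its end, so scheduled results during treatment = 0. A binder exception, and equally the calcitriol titration, would have no scheduled in-treatment result to act on.

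**3. What does the literal rule produce?**
- Calcium rises in a patient on calcium acetate: the study drug may be adjusted, but the calcium-containing binder stays at its dose unless the patient is withdrawn.
- Phosphate rises in a patient on sevelamer: the study drug may be adjusted, but sevelamer may not be raised unless the patient is withdrawn.

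**4. Is binder use recorded?**
- Section 5.9: 6 sociodemographic + 4 clinical + 3 biochemical = 13 variables; 0 name a binder.
- Case record form: 3 identification + 7 demographic + 4 clinical + 3 baseline biochemical + 3 week-12 + 11 adverse effect = 31 rows; 0 name a binder. The clinical block is numbered 1, 2, 4, 5 in the available text, so one row may have been lost.
- Baseline evaluation in section 5.11: demographics, comorbidities and the three laboratory values; no binder item.
- The adverse event table in the monitoring plan has a column for action taken. It could hold a change made for a recorded event, but not baseline use.

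**5. How many patients?** The protocol does not say how many will be on either drug at entry. The possible range is 0 to 98 (49 per arm × 2).

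**The case against.** Several points on the other side are fair.

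*The freeze protects the comparison.* The trial is unblinded: "It is an open-label study and both the researcher and the subject know about the drugs they are receiving". Allowing binder changes lets in decisions made knowing the arm. This stands as a real trade-off. It argues for a narrow exception with every change logged, not for having no exception.

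*Risk is already limited.* The baseline exclusions lower starting risk, and the study drug can be adjusted. This also stands and keeps the point modest. Neither provision allows a binder to be changed.

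*Withdrawal offers a route.* The adverse event definition includes laboratory abnormalities of clinical importance, the intolerance criterion ends in an open list, and management follows removal. Marked hypercalcaemia could be read into this chain. That stands in part, but the route works only by taking the patient out, and the listed examples are symptoms, not laboratory values.

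*Standard CKD treatment is continued in both arms.* A reader could take this to include usual binder adjustment. The sentence that names the two drugs and fixes their doses is the more specific text, so at best the protocol is ambiguous on a safety matter.

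*The wording matters less than the monitoring.* Without a week-6 result, an exception would have little effect. This stands, and the fix includes that test for this reason.

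*The missing binder fields are an omission.* Randomisation balances entry use in expectation, and a case record form row may be missing from the available text. This stands; the fields are a supporting addition only.

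**Conclusion.** The point holds as a rule fixed too rigidly. The protocol freezes two binders for 12 weeks without a safety exception, and no other section supplies one short of withdrawal. This concerns conduct and data collection, so a statistical analysis plan would not repair it. It is worth correcting but modest. It affects between 0 and 98 patients, and it rests on reading the binder sentence as written.

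Three stronger readings are tempting, and the documents support none of them.
- That the protocol bars safe care: it does not, because the study drug can be adjusted and patients can be withdrawn.
- That the PTH comparison is biased: the rule applies equally to both arms, allocation is randomised, and nothing in the text gives a direction or size of bias.
- That the missing binder fields are a separate error: section 5.9 and the baseline text are silent on binders, but this is an omission that makes the freeze hard to verify, not a mistake in its own right.

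**What to change.** Reword the sentence in section 5.11 along these lines: *Binders are kept stable in both arms unless a change is needed for clinically significant hypercalcaemia or hyperphosphataemia; every change is recorded with date and reason and reported by arm.*

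Measure calcium and phosphate at the existing week-6 visit, so that both this exception and the calcitriol titration have a result to act on. If interim monitoring is raised separately, this is the same test and should be counted once.

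As support, add binder type and dose to the case record form at baseline, and log later changes there.

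Cost: one sentence, two form fields plus a change log, and at most 98 × 1 = 98 extra calcium and 98 extra phosphate tests (196 in all), taking scheduled results per patient from 2 to 3. The downside is that a few binder changes may be made knowing the arm. They should be reported as a co-intervention when the calcium and phosphate outcomes are presented.
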